### 6.2.3. Subgroup Analysis

Sub-group analyses will be performed on the primary endpoint and key secondary endpoints for gender, baseline BMI (<30 vs ≥30), baseline weight (<75 kg vs ≥75 kg) and age group (<65 years vs ≥65 years).

Sub-group analysis will be based on ITT and PP analysis sets.

### 6.2.4. Sensitivity Analysis for the Primary Efficacy Endpoint

As a supplementary analysis, the primary analysis will be repeated on mITT analysis set and the per-protocol analysis set as defined in Section 3.4. In addition, a sensitivity analysis will be performed using multiple imputations method, when there are more than 5% early discontinuations from the study before week 16 due to reasons other than lack of efficacy or asthma-related AEs in either treatment group.

#### 6.2.4.1. Sensitivity Analysis Using Multiple Imputations

Patients who discontinued the treatment or the study before week 16 without LoAC due to lack of efficacy or asthma-related AEs will be considered as having experienced an LoAC, the same imputation method as used in the primary efficacy analysis.

For patients who discontinued the study before week 16 without LoAC for reasons other than lack of efficacy or due to asthma-related AEs, multiple imputations will be used from a Bernoulli distribution with the probability estimated from a logistic regression model from the observed LoAC data given the treatment group, sex, age group (<65 years vs ≥65 years), baseline FEV1, and baseline weight. A total of 100 datasets will be imputed and each will be analyzed with the logistic regression model the way as for the primary analysis. The final estimates will be obtained using Rubin’s method. The details are as follows:

**Step 1:** Estimate the probabilities for Bernoulli distribution

The SAS procedure in Section 6.2.2 will be used to obtain the probability estimates from a logistic regression model. The following statement will be added to SAS procedure:

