9.1. Sample Size and Power Considerations

The primary efficacy analysis for this study will be the comparison between treatment groups of the proportion of patients experiencing a LoAC event during the 16-week treatment period. The study will be considered positive if the primary efficacy test indicates a statistically significant treatment effect versus placebo at the predefined significance level.

Sample size calculations were performed based on the following considerations:

In the Phase 2a study results for dupilumab, the observed LoAC rate in the placebo group was 44% (Wenzel et al 2013). The patients in that study had elevated peripheral blood eosinophil counts (≥ 300 cells/ μL). To estimate the LoAC rate that would have been observed in patients with peripheral blood eosinophil counts < 300 cells/ μL , the ratio of exacerbation rates observed between eosinophil count strata in the placebo groups of the dupilumab Phase 3 study were used (Castro et al 2018). This resulted in an estimated LoAC rate of 27% for the patients meeting the entrance criteria for the current study.

This study is designed to detect a 60% reduction in LoAC rate versus placebo; ie, a placebo group rate of 27% and a TEV-48574 group rate of 10.8%.

Based on the assumptions above, and assuming a 15% dropout rate during the study, 62 randomized patients per treatment group will provide 80% power to detect a treatment effect of 60% reduction in LoAC rate in the TEV-48574 group using a Chi-square test with one-sided alpha (Type I error rate) of 0.1.

An unblinded interim analysis is planned to re-assess the sample size and conduct a futility analysis as described in Section 9.13. If the sample size increases as a result of the interim analysis, the number of evaluable patients would be expected to increase proportionately.

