#### *Treatment Period (16 weeks)*

The treatment period begins with randomization and ends with the EOT visit (week 16). After the end of the screening period, patients who meet all of the inclusion criteria, none of the exclusion criteria, and all of the randomization criteria will be randomized in a 1:1 ratio to the following regimens administered sc every 2 weeks:

- TEV-48574 [REDACTED]
- Placebo to match TEV-48574

With randomization, patients enter the 16-week treatment period. The patients will receive the IMP [REDACTED]

Patients should be observed for 2 hours after the end of the first (loading dose) and second (first maintenance dose) administration of IMP and for 1 hour after the subsequent IMP administrations.

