### **2.4. Sample Size and Power Considerations**

The primary efficacy analysis for this study will be the comparison between treatment groups of the proportion of patients experiencing a LoAC event during the 16-week treatment period. The study will be considered positive if the primary efficacy test indicates a statistically significant treatment effect versus placebo at the predefined significance level.

Sample size calculations were performed based on the following considerations:

In the Phase 2a study results for dupilumab, the observed LoAC rate in the placebo group was 44% (Wenzel et al 2013). The patients in that study had elevated peripheral blood eosinophil counts ( $\geq 300$  cells/ $\mu\text{L}$ ). To estimate the LoAC rate that would have been observed in patients with peripheral blood eosinophil counts  $< 300$  cells/ $\mu\text{L}$ , the ratio of exacerbation rates observed between eosinophil count strata in the placebo groups of the dupilumab Phase 3 study were used (Castro et al 2018). This resulted in an estimated LoAC rate of 27% for the patients meeting the entrance criteria for the current study.

This study is designed to detect a 60% reduction in LoAC rate versus placebo; ie, a placebo group rate of 27% and a TEV-48574 group rate of 10.8%.

Based on the assumptions above, and assuming a 15% dropout rate during the study, 62 randomized patients per treatment group will provide 80% power to detect a treatment effect of 60% reduction in LoAC rate in the TEV-48574 group with one-sided alpha (Type I error rate) of 0.1 with a Fisher's exact test.

An unblinded interim analysis is planned to re-assess the sample size and conduct a futility analysis as described in Section 13. If the sample size increases as a result of the interim analysis, the number of evaluable patients would be expected to increase proportionately.

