### 6.2.2. Primary Efficacy Analysis

The primary analysis will compare rates of LoAC between treatment groups using logistic regression with fixed effect for treatment, age group (<65 years vs  $\geq 65$  years) and gender, as well as baseline FEV1 and baseline weight as covariates. Patients who withdraw from the study before the week 16 or early terminated the study treatment due to lack of efficacy, LoAC, or an asthma-related adverse event will be analyzed as having experienced LoAC. Patients who withdraw from the study before the week 16 without LoAC or early terminated from the study treatment without experiencing LoAC during the patient's treatment period (Section 1.7) for other reasons will be analyzed as not experiencing LoAC. Asthma-related adverse events will be determined by blinded data reviews prior to the final database lock.

The treatment effect will be tested at a one-sided alpha of 0.1.

The primary analysis will be performed on the ITT analysis set. The rates of LoAC for each treatment group, confidence intervals, and p-value will be displayed.

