**ODS OUTUT ParameterEstimates=pest;**

Estimates from PROC GENMOD along with patients’ data will be used to calculate the probability, the p used for Bernoulli distribution, for each patient.

Observed data will be duplicated 100 times creating 100 sets of data. In each dataset, the SAS function **RAND(“Bernoulli”, p)** will be used to determine LoAC status (1=having LoAC, 0=not having LoAC) for patients with missing data due to reasons other than lack of efficacy or due to asthma-related AEs.

**Step 2:** Analysis

The 100 sets of data will be analyzed in a manner analogous to the analysis as described in Section 6.2.2 adding a by-statement for imputation to the SAS procedure.

The results from the 100 analyses will be combined using Rubin’s formulae in the following SAS procedure.

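### The multiple-imputation sensitivity analysis ignores how long a withdrawn patient had already been LoAC-free, so it imputes too many LoAC events and, if withdrawal differs between arms, biases the odds ratio

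*SAP*

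**What the plan says.** The primary analysis (SAP 6.2.2) counts patients who leave for other reasons as not having LoAC. SAP 6.2.4 adds a multiple-imputation analysis if more than 5% of either arm leave the study before week 16 for such reasons. For these patients SAP 6.2.4.1 states that "multiple imputations will be used from a Bernoulli distribution with the probability estimated from a logistic regression model from the observed LoAC data", given treatment, sex, age group, baseline FEV1 and baseline weight. Step 1 reuses the SAP 6.2.2 logistic code, which has no time or offset term, and turns its estimates into "the p used for Bernoulli distribution, for each patient". One Bernoulli draw with that p fills in each missing outcome. The 100 completed data sets are analysed with the primary logistic model and pooled by Rubin's rules.

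SAP 1.7 names proportions, adjusted proportions and odds ratios as the summaries of the primary endpoint. SAP 6.3.1 (time to LoAC) right-censors the same patients at withdrawal.

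**The concern.** A patient who leaves LoAC-free at day t lacks only the outcome from day t to week 16. The probability needed is therefore that of LoAC in the remaining time, given none so far. The SAP uses the probability for the whole period instead.

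The fitted p can also exceed even the whole-period risk. If withdrawn patients are left out of the fit, early LoAC cases stay in the data while LoAC-free leavers drop out of the denominator.

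This is the only imputation that the SAP specifies for the primary endpoint. Its purpose is to test the rule that leaving for other reasons means no LoAC. If it carries its own bias under independent withdrawal, agreement or disagreement with the primary result is hard to read.

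**Working it through.** **Inputs from the documents.** Design rates: "a placebo group rate of 27% and a TEV-48574 group rate of 10.8"% (SAP 2.4). Dropout and size: "assuming a 15% dropout rate during the study, 62 randomized patients per treatment group will provide 80% power" (SAP 2.4). Test: "using a Chi-square test with one-sided alpha (Type I error rate) of 0.1" (Protocol 9.1). Follow-up: 16 weeks (SAP 2.1).

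**Assumptions not in the documents.** Withdrawal is independent of LoAC. All 15% dropout is for other reasons. The LoAC hazard and the withdrawal rate are constant over 16 weeks (varied in step 5). Models are unadjusted.

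**1. The plan's own figure.** With p̄ = 0.189,
n = [1.2816·√(2·0.189·0.811) + 0.8416·√(0.27·0.73 + 0.108·0.892)]² / 0.162² = (0.7096 + 0.4559)² / 0.02624 = 51.8, so 52. Then 52/0.85 = 61.2, so 62 per arm. The stated size reproduces with the Chi-square basis.

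**2. Who is observed.** Let λ = −ln(1 − rate), μ = −ln(1 − 0.15) = 0.1625 and C = exp(−(λ+μ)). Observed LoAC is L = λ/(λ+μ)·(1 − C), LoAC-free withdrawal is W = μ/(λ+μ)·(1 − C), and LoAC-free completion is C.
- Placebo: λ = 0.3147; C = 0.73·0.85 = 0.6205; L = 0.2503; W = 0.1292.
- Active: λ = 0.1143; C = 0.892·0.85 = 0.7582; L = 0.0998; W = 0.1420.

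**3. Imputed against true remaining risk.** The SAP's p, with withdrawn patients left out of the fit, is L/(L + C). The true remaining risk is (rate − L)/W.

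| | SAP p | True remaining risk | Excess events in 62 |
|---|---|---|---|
| Placebo | 0.2503/0.8708 = 28.7% | 0.0197/0.1292 = 15.3% | 62·0.1292·0.135 ≈ 1.1 |
| Active | 0.0998/0.8580 = 11.6% | 0.0082/0.1420 = 5.8% | 62·0.1420·0.059 ≈ 0.5 |

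For a placebo patient who leaves at week 12, the true remaining risk is 1 − 0.73^(4/16) = 7.6%.

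The completed arm rate is L + W·p, which equals p itself: 28.7% and 11.6%, against 27% and 10.8%. Imputation thus returns the rate that simply dropping these patients would give.

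**4. Odds ratio.** It equals (L/C on active)/(L/C on placebo). The truth is (0.108/0.892)/(0.27/0.73) = 0.327.

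| Withdrawal, placebo/active | This imputation | Primary scoring | Truth |
|---|---|---|---|
| 15%/15% | 0.326 | 0.332 | 0.327 |
| 20%/10% | 0.307 | 0.355 | 0.327 |
| 25%/5% | 0.288 | 0.380 | 0.327 |
| 5%/25% | 0.370 | 0.290 | 0.327 |

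For example, 25%/5% gives (0.1053/0.8474)/(0.2364/0.5475) = 0.1243/0.4318 = 0.288.

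**5. Sensitivity to the assumptions.**
- If LoAC risk starts at week 4, when controller withdrawal begins, p is 28.3% against 18.7% on placebo and 11.4% against 7.1% on active.
- With withdrawal spread uniformly over 16 weeks, p is 28.8% against 14.9%, and 11.7% against 5.6%.
- If all withdrawal precedes any LoAC risk, there is no excess.
- If Step 1 keeps withdrawn patients in the fit as non-events, p = L, about 25% and 10%. The 25%/5% case then gives arm rates of 0.2364 + 0.2161·0.2364 = 28.7% and 0.1053 + 0.0473·0.1053 = 11.0%, an odds ratio of 0.307. The bias is smaller but in the same direction.

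**6. Simulation of the test** (62 per arm, 100 imputations, 6,000 replicates, uniform withdrawal, constant hazard, one-sided 0.1). With 15% in both arms, rejection is 83.7% for the SAP method and 83.4% for conditional imputation; under the null it is 9.7% for both. Under the null with 25%/5% withdrawal the SAP method rejects 15.9%, and with 5%/25% it rejects 5.4%. Conditional imputation gives 9.4% and 9.5%.

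**7. The fix recovers the truth.** Imputing with 1 − S(16)/S(t) returns 27.0% and 10.8%, with an odds ratio of 0.327.

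**The case against.** The strongest reply is that the planned effect measure is the odds ratio, and with equal withdrawal it is right: 0.326 against 0.327, with unchanged rejection rates. A reader might infer that the analysis favours the drug, because the risk difference rises from 16.2 to 17.1 points. The documents do not support that. No risk difference is planned for LoAC, and the odds-ratio bias runs for or against the drug according to which arm loses more patients. This part of the reply stands.

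A reader might also infer that this is the only check on the rule for other-reason withdrawals. It is not. SAP 6.3.1 censors these patients and so uses their time at risk. The per-protocol repeat (SAP 3.4 and 6.2.4) excludes patients who missed doses for reasons unrelated to LoAC. Protocol Appendix J foresees Cox models and imputation for COVID-19 attrition. This also stands, although the per-protocol repeat shares the selection of dropping these patients.

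The size is modest: about 1.1 and 0.5 excess events in 62 per arm at 15% withdrawal, and fewer near the 5% trigger. Step 1 also does not say whether withdrawn patients are left out of the fit, so 28.7% and 11.6% hold for one reading only. Under the other reading p is still too high.

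**Conclusion.** The concern holds in this form: the imputation ignores time already spent LoAC-free and over-imputes LoAC in both arms, by roughly a factor of two in p in the base case. The arm proportions, a planned summary, are overstated by about 1.7 points on placebo and 0.8 on active. The odds ratio and its test are essentially untouched when withdrawal is equal. When withdrawal is unequal, the odds ratio is biased in a direction set by the imbalance (0.288 or 0.370 against 0.327 at 25%/5% and 5%/25%), opposite to the bias of the primary scoring in the cases shown. That is the situation in which a sensitivity analysis is most needed.

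The size rests on the design rates, independent withdrawal, the assumed hazard shape and timing, and all dropout being for other reasons. It shrinks to zero if withdrawal comes before any LoAC risk. The analysis runs only above the 5% trigger, but the planned 15% dropout makes that likely. The primary test does not depend on it.

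**What to change.** In SAP 6.2.4.1, replace the logistic p in Step 1. Fit a time-to-LoAC model (piecewise-exponential or Cox) with treatment, sex, age group, baseline FEV1 and baseline weight, with other-reason withdrawals censored at their withdrawal day. Impute LoAC for each such patient with probability 1 − S(16 weeks)/S(withdrawal day), using that patient's predicted survival curve. Then run the planned logistic model on each data set and pool as now. Entering withdrawn patients as censored also settles whether they belong in the fit.

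The LoAC and withdrawal dates are already derived for SAP 6.3.1, so no new data are needed. The cost is a SAP text change, modest extra programming and reliance on a hazard model. The primary analysis stays as it is.

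### The multiple-imputation sensitivity analysis keeps the logistic coefficients fixed across its 100 datasets, so its pooled standard error is slightly too small

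*SAP*

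**What the plan says.** SAP 6.2.4 adds a multiple-imputation analysis of the primary endpoint, to be run "when there are more than 5% early discontinuations from the study before week 16 due to reasons other than lack of efficacy or asthma-related AEs"; one arm above that limit is enough. SAP 6.2.4.1 then sets out the algorithm:

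- **Model.** Missing outcomes are drawn so that "multiple imputations will be used from a Bernoulli distribution with the probability estimated from a logistic regression model from the observed LoAC data", given treatment, sex, age group, baseline FEV1 and baseline weight.
- **Probability.** The primary-analysis procedure is run and its parameter estimates are saved. "Estimates from PROC GENMOD along with patients’ data will be used to calculate the probability, the p used for Bernoulli distribution, for each patient".
- **Copies.** "Observed data will be duplicated 100 times creating 100 sets of data".
- **Draw.** In each copy the SAS Bernoulli random function, evaluated at that p, "will be used to determine LoAC status (1=having LoAC, 0=not having LoAC) for patients with missing data".
- **Pooling.** "The results from the 100 analyses will be combined using Rubin’s formulae in the following SAS procedure", which is PROC MIANALYZE.

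Neither the SAP nor the protocol describes a draw of the coefficients, a refit for each copy, or an imputation routine that would do either.

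**The concern.** Rubin's total variance is the average within-imputation variance plus a between-imputation term. The second term must carry everything that is unknown about the missing outcomes: the randomness of each outcome given its probability, and the uncertainty about the probability itself. Here the probability comes from a logistic model fitted to roughly a hundred patients and is then treated as known. The second source is left out, which makes the imputation improper in Rubin's sense, and the pooled variance is too small.

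The SAP gives an explicit sequence of steps, so a programmer who follows it will produce this result; it is not a detail left open. What is at stake is the credibility of a check on missing outcomes. The primary analysis scores other-reason dropouts as free of LoAC, and this is the only fully specified ITT analysis of the binary endpoint that imputes them instead. It should not understate the uncertainty that it exists to show, and the understatement grows with the amount of missing data.

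**Working it through.** **1. Scenario, and the plan's own figure.** SAP 6.2.4.1 states no standard error, so the check uses the sample-size scenario (protocol 9.1, SAP 2.4): LoAC 27% vs 10.8%, one-sided alpha 0.1, 80% power, 15% dropout, 62 randomized per arm. With the protocol's chi-square test and pooled rate (0.27 + 0.108)/2 = 0.189:

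n = [1.2816·√(2·0.189·0.811) + 0.8416·√(0.27·0.73 + 0.108·0.892)]² / 0.162² = (0.7096 + 0.4559)² / 0.026244 = 51.8, so 52 per arm.

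52/0.85 = 61.2, so 62. Power at 52 per arm is 80.1%. The stated figure is reproduced.

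**2. What varies between the 100 datasets.** One fit gives one coefficient vector and one p per patient. The copies are made afterwards, so only the Bernoulli draw differs.

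**3. Analytic size.** Scale the complete-data variance of the log odds ratio to 1 and let f be the fraction of missing information. With many imputations:

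- Coefficients drawn (proper): between-imputation variance f/(1−f); total 1 + f/(1−f) = 1/(1−f).
- Coefficients fixed (SAP): between-imputation variance f; total 1 + f.
- Variance ratio (1+f)(1−f) = 1−f²; standard-error ratio √(1−f²).

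If data are missing completely at random and equally in both arms, f is close to the share imputed: √0.9975 = 0.9987 at 5%, √0.9775 = 0.9887 at 15%, √0.91 = 0.9539 at 30%.

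**4. Simulation of the SAP steps.** Setup: 62 per arm, 100 imputations, 1,500 trials per row. The model has treatment, two continuous and two binary covariates (prevalence 20% and 60%), with no covariate effect on LoAC and data missing completely at random. Near-separated samples were dropped (1.1% to 4.5% of trials in these rows). The comparator draws the coefficients from a normal distribution with the estimated mean and covariance before each imputation.

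| Share imputed | Mean SE, fixed | Mean SE, drawn | Mean SE ratio | √(1−f²) | Between-imputation variance, fixed/drawn |
|---|---|---|---|---|---|
| 5% | 0.5580 | 0.5586 | 0.999 | 0.9987 | 0.85 |
| 15% | 0.5977 | 0.6040 | 0.990 | 0.9887 | 0.76 |
| 30% | 0.6352 | 0.6634 | 0.958 | 0.9539 | 0.66 |

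The standard error is thus understated by about 0.1%, 1.0% and 4.2%. With 500 per arm the ratios at 15% and 30% were 0.990 and 0.956.

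A second check: the fixed-coefficient standard error also fell below that of the plain logistic fit to the observed patients (ratio 0.991 at 15%, 0.961 at 30%). Imputing from the same model and covariates adds no information on treatment, so that gain in precision is spurious.

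**5. Effect on the test.** With 27% in both arms and 3,000 trials, one-sided rejection at a nominal 10% was:

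- 15% imputed: 11.4% fixed, 10.8% drawn.
- 30% imputed: 12.3% fixed, 10.7% drawn.

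The Monte Carlo standard error of each rate is about √(0.11·0.89/2990) = 0.6 points. Both methods used the same simulated trials, so their difference is better determined than that.

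For a borderline correct p of 0.100 (z = 1.2816), a 1% shortfall gives z = 1.2816/0.99 = 1.2945 and p = 0.098. A 4.2% shortfall gives z = 1.2816/0.958 = 1.338 and p of about 0.090.

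**The case against.** The strongest reply is that nothing in the trial turns on this. SAP 2.4 declares the study positive on the primary test alone, and that test uses no multiple imputation. The analysis in question is conditional, has no success criterion, and near its 5% trigger the error is about 0.1%. All of that stands, and it fixes how serious the point is.

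Several stronger readings are tempting, and the documents do not support them:

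- **That this is the only planned analysis that does not score dropouts as free of LoAC.** The time-to-LoAC analysis (SAP 6.3.1) right-censors other-reason withdrawals. The per-protocol set (SAP 3.4), on which the primary analysis is repeated, excludes patients who missed doses for reasons not related to LoAC. Protocol Appendix J also allows imputation for COVID-19 attrition, without giving a method.
- **That the error always flatters the drug.** A smaller standard error moves z away from zero in either direction. If the estimate favours placebo with z = −0.5, the one-sided p goes from 0.691 to 0.693 with a 1% smaller standard error. Nor is the fixed-coefficient standard error smaller in every realised trial: in a separate run of about 480 trials per scenario it was smaller in about 77% at 15% missing and about 95% at 30%. Systematic is the right word.
- **That 15% of patients will be imputed.** The imputation covers only those who leave the study before week 16 without LoAC and for other reasons. The 15% is dropout during the study as a whole, and patients who stop IMP may stay in the study (protocol 4.4.2). Appendix J does attach 15% to early termination for reasons other than loss of asthma control, so the figure is plausible, but the share that meets the imputation rule is not given.

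None of this touches the mechanism. No document supplies the missing coefficient draw.

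**Conclusion.** The point holds as a small technical error in a stated procedure. As written, SAP 6.2.4.1 is improper imputation pooled by a formula that assumes proper imputation. The pooled standard error is systematically too small and the interval too narrow, and the one-sided p-value is too small when the estimate favours TEV-48574.

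The analytic result and the simulation agree on size: about 0.1% at 5% imputed, 1% at 15% and 4% at 30%. These figures rest on the planning rates, 62 per arm, data missing completely at random and covariates unrelated to LoAC. The three shares are assumptions: 5% is the trigger, 15% the planned total dropout, and 30% twice the plan.

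A reader might infer that the trial's conclusion is at risk. It is not: the primary test, the sample size and the interim rules do not use this analysis. It is worth correcting because the correction is almost free.

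**What to change.** In SAP 6.2.4.1, Step 1, save the estimated covariance matrix along with the parameter estimates. For each of the 100 imputations, draw a coefficient vector from the normal distribution with those estimates and that covariance, compute each patient's p from the draw, then draw the Bernoulli value. Using PROC MI with its logistic method, or refitting the model on a bootstrap sample before each imputation, would serve equally well. The analysis of each dataset and the pooling in PROC MIANALYZE stay as planned.

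The cost is one or two sentences in the SAP, a few lines of code and slightly wider intervals. No new data are needed, and the primary analysis and sample size do not change.
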